10.3 DURATION VARIABLES

Study day 0 is the day the subject receives CTR-US or mOCTR. Postoperative study day will be calculated relative to day 0 as follows:

Study Day = (Date of Event - Date of Treatment)

10.4 ANALYSIS WINDOWS

Study data will be categorized into discrete, contiguous reporting windows to ensure that all available data are included in the analyses. The analysis windows for this study are defined below:

Study Visit	Target Days	Analysis Window
Treatment	0	0
2 weeks	14	7-22
1 month	30	23-60
3 months	90	61-135
6 months	180	136-270
12 months	365	271-450

10.5 DATA ANALYSIS METHODS

Baseline data will be analyzed using descriptive statistics. Continuous data will be summarized using mean and standard deviation for normally distributed data, median and interquartile range for non-normally distributed data, and counts and percentages for categorical data. For categorical variables, percentages will be calculated based on non-missing data.

The percentage of patients in each treatment group that return to normal daily activities within 3 days postoperatively, and the percentage of employed patients in each treatment group that return to work within 3 days postoperatively will be reported and compared using the Fisher's exact test. These outcomes will also be reported as the median and interquartile range in each treatment group. Due to the likelihood that the data distribution may be positively skewed, the nonparametric Mann-Whitney U test will be the statistical test used to assess these endpoints.

Differences between the CTR-US and mOCTR groups with respect to longitudinally measured continuous outcomes (i.e. BCTQ-SSS, BCTQ-FSS, Numeric Pain Scale, EQ-5D-5L) will be analyzed using mixed model analysis and adjusting for the baseline score.

Adverse events will be reported using counts, percentages and exact 95% confidence intervals using Clopper-Pearson's method. The incidence of AEs in each group will be calculated on a per-subject basis and analyzed using Fisher's exact test.

Statistical analyses will be performed using a two-sided hypothesis test at a 5% level of significance. No adjustments for multiplicity are planned. Missing data imputation will not be performed.

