7.1.2 Time to Return to Work Among Employed Subjects

Among study subjects who report full-time or part-time employment, time to return to work will be ascertained through the ViedocMe ePRO module by asking whether the subject has returned to work in full or limited capacity. Return to work within 3 days postoperatively will represent a secondary endpoint of the study. The time to return to work will be defined as the number of days between treatment and the time the subject reports returning to work in any capacity.

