10.1 SAMPLE SIZE JUSTIFICATION

The results of the power analysis provided a sample size consisting of 102 evaluable subjects. Group sample sizes of 68 and 34 achieve 80% power to reject the null hypothesis of zero effect size when the population effect size is 0.60 and alpha is 0.05 using a two-sided two-sample equal-variance t-test with a 2:1 randomization allocation. To account for reasonable subject attrition, 120 subjects (n≈80 CTR-US, n≈40 mOCTR) will be enrolled in the trial.

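### Return to normal activities is compared with tests that use no baseline information, so a cheap precision gain may be forgone; its size rests on a correlation the documents do not give

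*Combined protocol and SAP*

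**What the plan says.** Section 10.5 sets the analysis of the two return outcomes. The percentages returning within 3 days, to activities and (among the employed) to work, "will be reported and compared using the Fisher's exact test". The times are summarised by median and interquartile range, and "the nonparametric Mann-Whitney U test will be the statistical test used to assess these endpoints". No covariate is named for either. The four longitudinal scales (BCTQ-SSS, BCTQ-FSS, Numeric Pain Scale, EQ-5D-5L), by contrast, "will be analyzed using mixed model analysis and adjusting for the baseline score".

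The patient-reported table in Section 6.7 ticks all four scales at baseline. Return to activities is first asked on postoperative days 1 to 14, so it has no baseline value of its own.

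No outcome is labelled primary. Return to activities within 3 days heads the synopsis list and Section 7.1. It is also the only main outcome whose own subsection names no secondary endpoint; for work, for example, Section 7.1.2 states "Return to work within 3 days postoperatively will represent a secondary endpoint of the study". It is therefore primary by implication only.

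Section 10.1 is not tied to any endpoint: "Group sample sizes of 68 and 34 achieve 80% power to reject the null hypothesis of zero effect size". The sizing conditions behind this statement, which include no covariate, are given as follows: "when the population effect size is 0.60 and alpha is 0.05 using a two-sided two-sample equal-variance t-test". On attrition the section adds: "To account for reasonable subject attrition, 120 subjects (n≈80 CTR-US, n≈40 mOCTR) will be enrolled in the trial".

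**The concern.** A subject's function and pain before surgery may well influence how soon they report being back to normal. Section 6.6 tells subjects to resume activity as pain, function and wound healing allow, and two of those three have a baseline measure. If the baseline scores are prognostic, an analysis that ignores them leaves explainable variation in the comparison. With only 34 evaluable mOCTR subjects planned, that variation includes whatever chance imbalance arises between the arms.

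What is at stake is precision on the outcome that heads the list. It could be gained with no new data and no extra subjects. It has to be prespecified, because an adjusted analysis added once the data have been seen would be post hoc in an unblinded, self-reported trial.

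**Working it through.** **1. The plan's own figure.** Inputs from Section 10.1: effect size 0.60, two-sided alpha 0.05, groups of 68 and 34, unadjusted t-test. The noncentrality is 0.60 / sqrt(1/68 + 1/34) = 0.60 / 0.2100 = 2.857 on 100 degrees of freedom, which gives power 80.8%. Groups of 66 and 33 give 79.6%, so 102 is the smallest 2:1 total that reaches 80%. Going from 102 to 120 allows 1 − 102/120 = 15% attrition. The figure reproduces, and it assumes no adjustment.

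**2. Effect of a prognostic covariate on that scale.** Adjustment multiplies the residual variance by (1 − rho²), so the effect size becomes 0.60 / sqrt(1 − rho²). Here rho is the correlation between baseline information and outcome. It is an assumption throughout.

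| rho | power at 68/34 | evaluable N for 80% |
|---|---|---|
| 0 | 80.8% | 102 |
| 0.2 | 82.3% | 99 |
| 0.3 | 84.3% | 93 |
| 0.4 | 87.0% | 87 |
| 0.5 | 90.4% | 78 |

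Neither return outcome is analysed by t-test, so these figures only set the scale.

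**3. Days to return.** Trials of 68 and 34 subjects were simulated with a shift of 0.6 SD on a normal (log-time) scale and one covariate, 4,000 trials per setting, error about ±1.5 points.

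| rho | Mann-Whitney | rank ANCOVA | gain, points |
|---|---|---|---|
| 0 | 79.9% | 80.0% | 0.1 |
| 0.2 | 78.2% | 79.8% | 1.6 |
| 0.3 | 79.4% | 82.3% | 2.9 |
| 0.5 | 78.6% | 88.8% | 10.2 |

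A separate set of runs gave 78% against 80% at rho 0.3 and 79% against 87% at rho 0.5. The range is therefore about 2 to 3 points and 8 to 10 points. With no treatment effect, rank ANCOVA rejected in 4.6% to 5.2% of trials.

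**4. Return within 3 days.** The registry median for CTR-US in Section 5 is 3 days (IQR 2 to 5), so about 50% return by day 3. The mOCTR rate is not given. The same 0.6 SD shift implies Φ(−0.6) = 27%. If whole-day reporting puts the cut at 3.5 days, the log-scale SD is ln(2.5)/1.349 = 0.679. The rates are then Φ(ln(3.5/3)/0.679) = Φ(0.227) = 59% and Φ(0.227 − 0.6) = 35%.

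Linear risk-difference test without and with the covariate:

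| rho | 50% vs 27% | 59% vs 35% |
|---|---|---|
| 0 | 61.5% → 59.8% | 59.8% → 59.6% |
| 0.3 | 60.6% → 61.4% | 60.7% → 64.1% |
| 0.5 | 61.3% → 67.0% | 60.0% → 68.3% |

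A further set of runs put the covariate gain at about 0 points at rho 0.3 and 4 at rho 0.5. The range is about 0 to 3 and 4 to 8 points. The 1.7-point drop at rho 0 in the first column is close to simulation error.

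Fisher's test itself had 55% to 56% power at 50% vs 27%, with a null rejection rate of 3.5% to 3.8%. A logistic model with a standardized risk difference and two covariates (59% vs 35%, 3,000 trials) gave 66% at rho 0, 67% at 0.3 and 71% at 0.5, against 56% to 58% for Fisher. Most of the gap to Fisher is already there with useless covariates. It reflects Fisher's conservatism, not baseline information, and is not counted in the gain.

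**5. Return to work within 3 days.** With the registry's 62% employed, 102 × 0.62 ≈ 63 subjects, or about 42 and 21. The registry lower quartile is 3 days, so about 25% of CTR-US subjects return by then. The 0.6 SD shift gives Φ(−0.674 − 0.6) ≈ 10% for mOCTR, or 21 × 0.10 ≈ 2 events. The chance of none is 0.90^21 ≈ 11%. In simulation an ordinary logistic model failed in about 10% of such trials. With 25% in both arms it rejected in 6.8% to 7.5%, against 3.0% to 3.8% for Fisher.

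**The case against.** The strongest reply is that nothing planned is wrong. The 102 was sized on an unadjusted test, and no document shows that baseline function or pain predicts return. Section 6.6 concerns pain and function after surgery, not before. All of this stands, and it limits the claim to a possible gain.

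Four stronger readings are tempting, and the documents do not support them.

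- **That the trial loses power it claims to have.** Leaving out covariates does not lower the 80% in Section 10.1. Chance imbalance is already covered by the tests' type I error and is not a bias.
- **That Section 10.5 contradicts itself by adjusting the scales but not the return outcomes.** Each scale is adjusted for its own baseline value, and return to activities has none. The comparison shows only that the plan accepts baseline adjustment in principle.
- **That power would rise to about 90%.** That is a t-test figure at an assumed rho of 0.5. For the 3-day proportion, which heads the synopsis list, the covariate gain at rho 0.3 may be nil.
- **That one logistic model should serve every 3-day outcome.** Step 5 shows it would be unreliable for return to work.

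It is also fair to say that the choice of Fisher's test, and the gap between it and the t-test used for sizing, may matter more for the 3-day outcome than covariates do. Exact Fisher power at 68/34 is 83.7% for 50% vs 20%, but 44.8% for 50% vs 30%. That is a separate matter, as is the use of site, the randomization stratum.

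**Conclusion.** The point holds as a missed opportunity, not as an error. The planned tests for return to normal activities use none of the baseline information the trial collects. If that information is prognostic, precision is forgone.

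The gain in days to return is about 2 to 3 points of power at rho 0.3 and 8 to 10 at rho 0.5. In the 3-day proportion it is about 0 to 3 and 4 to 8 points from the covariates themselves. At rho 0 there is essentially no loss.

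These sizes rest on an assumed rho, an effect of 0.6 SD, CTR-US rates taken from the registry, an assumed mOCTR rate, and simulations with no site differences. Most simulations used a single covariate standing for function and pain together. A modest benefit is the reasonable expectation. The case for acting rests mainly on the low cost.

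**What to change.** In Section 10.5, prespecify:

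- **Days to return to normal activities:** a rank ANCOVA with baseline BCTQ-FSS and baseline Numeric Pain Scale as covariates.
- **Return to normal activities within 3 days:** a covariate-adjusted (standardized) risk difference with a robust 95% CI, using the same two covariates.
- **Supportive analyses:** the unadjusted Mann-Whitney and Fisher results for both.
- **Return to work within 3 days among the employed:** keep Fisher's exact test, or use a sparse-data method such as Firth logistic regression with a stated fallback if it cannot be fitted.

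The cost is a few sentences in Section 10.5. No data collection, visit or sample size changes. The downsides are that a model must be fitted and that there is a negligible loss if the baseline scores turn out not to be prognostic.

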1. PROTOCOL SYNOPSIS

Title	Trial of Ultrasound guided carpal tunnel release versus Traditional Open Release (TUTOR)					
Purpose	To compare the safety and effectiveness of carpal tunnel release with ultrasound guidance (CTR-US) vs. mini-open carpal tunnel release (mOCTR) in patients with symptomatic carpal tunnel syndrome (CTS)					
Study Design	Multicenter randomized controlled trial of subjects with symptomatic CTS who will be randomized in 2:1 fashion to treatment with CTR-US or mOCTR					
Enrollment	120 subjects will be enrolled in the study and randomized (2:1) to CTR-US (n≈80) or mOCTR (n≈40)					
Visit	Post procedure remote subject-reported outcomes visits:					
Schedule	1-14 days; 1, 3, 6, and 12 months					
Clinical Sites	Up to 12 investigational sites located within the United States					
Inclusion Criteria	 ≥18 years of age Clinical diagnosis of unilateral or bilateral idiopathic CTS CTS-6 score ≥12 in target hand Absence of carpal tunnel symptoms in the contralateral hand that interfere with normal daily activities or work at the time of consent and are not anticipated to interfere with return to activities or return to work within at least 3 months post-operatively Median nerve cross-sectional area ≥10 mm² in the proximal carpal tunnel region of the target hand measured by diagnostic ultrasound Prior failure of one or more nonsurgical treatment options for the target hand (e.g., physical activity modification, bracing, splinting, corticosteroid injection) Subject agrees to complete follow-up questionnaires over a 12-month period Subject has a valid mobile phone number and email address to receive and answer follow-up questionnaires 					

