6. STUDY PROCEDURES

6.1 INVESTIGATIONAL SITE SELECTION

Investigational sites will be selected based on the availability of the subject pool to be included in the study, the ability of the study site to perform the research in compliance with the investigational plan, and agreement to comply with the institutional review board (IRB) requirements. All investigators will be board certified orthopedic or plastic surgeons experienced in the diagnosis and treatment of CTS, including CTR-US and mOCTR. Each surgeon will complete a structured training program in musculoskeletal ultrasound including ultrasound machine controls, sonographic anatomy of the carpal tunnel region, identification and cross-sectional measurement of the median nerve, and CTR-US using the UltraGuideCTR device. In addition, all investigators must have treated a minimum of 10 procedures using CTR-US and 10 patients using mOCTR prior to treating subjects in the clinical trial.

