6.3 RANDOMIZATION

Subjects meeting all study inclusion/exclusion criteria after their screening evaluation will be randomized. This study will enroll 120 subjects who will be randomized in 2:1 fashion to receive CTR-US (n≈80) or mOCTR (n≈40). The randomization sequence for this trial will be computer-generated by the electronic data capture system (Viedoc). The randomization

sequence will be stratified by site with variable block sizes. Treatment assignment will be concealed until it is presented to authorized site personnel at the time of randomization. Only randomized and treated subjects will be considered enrolled in the study. Randomized patients who do not receive their assigned treatment will be discontinued from the trial.

6.4 **BLINDING**

Owing to obvious differences in surgical technique, it is not possible to blind the treating physicians. Owing to notable visual differences in the postoperative scar between surgical techniques (3-5 mm for CTR-US and approximately 3 cm for mOCTR), it is not possible to blind the subjects. Owing to the fact that all data collected in this trial will be self-reported, it is not possible to blind outcome assessors (i.e., subjects).

6.5 **PROCEDURE**

The key procedural steps involved in CTR-US are listed below.

- 1. Using direct US visualization, identify relevant anatomical structures within the carpal tunnel.
- 2. Dissect synovial tissue from the undersurface of the TCL via hydrodissection.
- 3. Insert the device through a small wrist incision and advance into the carpal tunnel.
- 4. Position the tip of the device distal to the distal TCL so that the TCL Blade will engage the distal TCL.
- 5. Confirm the position of the device under ultrasound.
- 6. Activate the Stealth MicroGuard balloons to create space within the carpal tunnel.
- 7. Deploy the TCL Blade by moving the slide button proximally to transect the TCL from distal to proximal until the TCL Blade passes into its proximal recessed position.
- 8. With the device or an elevator, probe the TCL to ensure a complete release.

Complete procedural details are provided in the Instructions for Use (https://sonexhealth.com/physicians/ultraguidectr/instructions-for-use).

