6.6 POST-TREATMENT ASSESSMENTS

Postoperative patient care instructions will be standardized for each treatment group and among all participating sites to minimize bias. Investigators will instruct subjects to "participate in activities and return to work, as tolerated, based on pain, function, and wound healing status".

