7.2 ADDITIONAL OUTCOMES

Additional outcomes of the study will include:

- Median time to return to normal activities
- Median time to return to work
- BCTQ-SSS change at 2 weeks, 1 month, 6 months, and 12 months
- BCTQ-FSS change at 2 weeks, 1 month, 6 months, and 12 months
- Numeric Pain Scale change at 2 weeks, 1 month, 6 months, and 12 months
- EQ-5D-5L change at 2 weeks, 1 month, 6 months, and 12 months
- Device- or procedure-related AEs at 2 weeks, 1 month, 6 months, and 12 months
- Serious device- or procedure-related AEs at 2 weeks, 1 month, 3 months, 6 months, and 12 months

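### Randomisation is stratified by site, but 10.5 names no site term for the mixed model; if site is left out and sites differ, the reported standard errors are too large

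*Combined protocol and SAP*

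**What the plan says.** Section 6.3 states that the randomisation "sequence will be stratified by site with variable block sizes". The Protocol Synopsis allows "Up to 12 investigational sites located within the United States".

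Section 10.5 says that the four longitudinal continuous outcomes "will be analyzed using mixed model analysis and adjusting for the baseline score". The baseline score is the only model term named. No random effects are listed, and no other section brings site into the analysis. The 3-month changes in these outcomes are called secondary endpoints in 7.1.3 to 7.1.6. Section 7.2 adds further time points for each, for example "BCTQ-SSS change at 2 weeks, 1 month, 6 months, and 12 months".

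The sample size in 10.1 was calculated "using a two-sided two-sample equal-variance t-test with a 2:1 randomization allocation", so site plays no part there either.

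Two provisions may keep sites alike. Section 6.1 requires that "all investigators must have treated a minimum of 10 procedures using CTR-US and 10 patients using mOCTR" before treating trial subjects, alongside a structured training programme. Section 6.6 says: "Postoperative patient care instructions will be standardized for each treatment group and among all participating sites to minimize bias".

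**The concern.** Blocking within site keeps the arms at roughly 2:1 in every site, so differences between sites largely cancel from the treatment comparison. A model without site does not know this. It counts the between-site variation as error and reports a standard error larger than the estimate's real sampling variation. Confidence intervals are then too wide, and the test rejects less often than its nominal 5%.

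Two conditions must both hold: site is in fact left out, and sites differ after baseline adjustment. The text settles neither. A mixed model may carry only a subject effect, or a site effect as well, and two analysts could read 10.5 differently. In a trial where 6.4 rules out blinding, that choice is better made before the data are seen.

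**Working it through.** **Inputs from the documents.** 68 and 34 evaluable subjects, effect size 0.60, two-sided alpha 0.05 and 120 enrolled (10.1); up to 12 sites (Synopsis); stratification by site (6.3). The share remaining evaluable is 102/120 = 85%.

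**Assumed, because the documents give no figure.** Site ICC of 0, 0.05, 0.10 and 0.20.

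**Step 1: the plan's own figure.** With unit SD, SE = √(1/68 + 1/34) = 0.210, so the noncentrality is 0.60/0.210 = 2.857. On 100 degrees of freedom, the two-sided noncentral t gives power of 80.8%. A split of 66 and 33 gives 79.6%. The stated 80% reproduces.

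**Step 2: approximation at a single time point.** Without site, the reported variance is about σ²(1/68 + 1/34). With the arms balanced within site, the true variance is about σ²(1 − ICC)(1/68 + 1/34). The reported SE is therefore too large by the factor 1/√(1 − ICC):
- ICC 0.05: 1/√0.95 = 1.03
- ICC 0.10: 1/√0.90 = 1.05
- ICC 0.20: 1/√0.80 = 1.12

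Power at 0.60 SD without site is 80.9, 81.5, 82.1 and 83.5% at ICC 0, 0.05, 0.10 and 0.20. With 12 fixed site effects it is 80.7, 82.6, 84.6 and 88.5%. Power without site does not fall as sites diverge; it only rises less than it could.

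**Step 3: simulation of the longitudinal model.** 5000 runs per setting (Monte Carlo error at most about 0.6 points), testing the 3-month contrast in a REML model with visit, treatment by visit, baseline score and a random subject intercept. Further assumptions:
- 12 sites of 10, with permuted 2:1 blocks of 3 or 6 within site
- baseline-to-follow-up correlation 0.5, and between-visit residual correlation 0.6
- random dropout leaving 93, 89, 85, 80 and 75% at the five visits

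| ICC | Reported SE / empirical SD, no site | Same, random site | Null rejection, no site / random site | Power at 0.60 SD, none / random / fixed site | Power at 0.50 SD, none / random / fixed site |
|---|---|---|---|---|---|
| 0 | 0.1791/0.1800 | 0.1781/0.1801 | 5.0 / 5.1% | 90.9 / 91.1 / 90.3% | 78.6 / 78.9 / 78.0% |
| 0.05 | 0.1803/0.1768 | 0.1753/0.1766 | 4.5 / 5.1% | 91.1 / 92.0 / 91.6% | 79.0 / 80.7 / 80.3% |
| 0.10 | 0.1808/0.1709 | 0.1708/0.1698 | 4.0 / 5.0% | 91.4 / 93.3 / 93.1% | 79.7 / 83.2 / 83.2% |
| 0.20 | 0.1821/0.1642 | 0.1612/0.1607 | 3.2 / 5.1% | 92.7 / 95.9 / 95.6% | 80.8 / 87.4 / 87.1% |

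The no-site ratios are 0.995, 1.020, 1.058 and 1.109, so the reported SE is about 0, 2, 6 and 11% too large. With random site it is within about 1%. The random-site gain in power for ICC 0.05, 0.10 and 0.20 is 0.9, 1.9 and 3.2 points at 0.60 SD, and 1.7, 3.5 and 6.6 points at 0.50 SD. The 0.50 SD setting is not from the plan; it was chosen to sit near 80% power after baseline adjustment.

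**Step 4: what actually improves.** From no site to random site, the empirical SD goes from 0.1768 to 0.1766, from 0.1709 to 0.1698 and from 0.1642 to 0.1607. These are reductions of 0.1, 0.6 and 2.1%. The estimate itself hardly becomes more precise; mainly, its reported SE becomes correct.

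**Step 5: other settings.** With 12 uneven sites (24 subjects down to 2) and 0.50 SD, power with none / random / fixed site is 78.2 / 78.5 / 77.2% at ICC 0 and 79.0 / 85.8 / 86.0% at ICC 0.20. With 6 sites of 20 it is 79.4 / 79.4 / 79.1% and 79.9 / 86.8 / 86.6%. If site effects also shift the baseline score (assumed correlation 0.5), random site cuts the reported SE by 2.2, 4.3 and 8.9% at ICC 0.05, 0.10 and 0.20, against 2.8, 5.5 and 11.5% otherwise. A separate ANCOVA simulation (12 sites of 10, 85% present) gave null rejection without site of 5.0, 4.3, 3.7 and 2.9% across the four ICCs, which agrees in direction and rough size.

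**The case against.** The strongest case against is that nothing may be wrong. A mixed model can already include a site effect, and 6.1 and 6.6 give reason to expect similar sites. Both points stand, which is why the consequence is doubly conditional. They do not settle what 10.5 intends.

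The gain is also small. At the plan's own 0.60 SD, power without site is already above 90% in the simulation, and random site adds about 1 point at ICC 0.05 and 2 at 0.10. Within-site balance is not exact either: small sites leave blocks unfilled, and 10.2 drops subjects not treated as assigned. The simulation includes unfilled blocks but not those exclusions. These objections stand and limit the weight of the point.

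Site is not the only unstated term. Visit, treatment by visit, covariance structure and degrees of freedom had to be assumed above. Naming site therefore closes one choice, not all of them.

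A reader might go further and infer that the 3-day proportions, return times and adverse events also need site-stratified tests. The calculations do not support that. For the 3-day proportion, the power of a Cochran-Mantel-Haenszel test with small sites pooled, minus that of an unstratified chi-square test, was −1.1, −0.5, −0.1 and +2.4 points across the four ICCs. Among employed subjects (assumed 62%, as in the section 5 registry) it was −1.0, −1.0, −0.6 and −0.1. No calculation supports a van Elteren test for the return times. For adverse events 10.5 says: "The incidence of AEs in each group will be calculated on a per-subject basis and analyzed using Fisher's exact test". The registry in section 5 recorded 1 complication among 346 patients; with counts that low, stratifying would add little.

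**Conclusion.** The point holds as a low-priority improvement. Section 6.3 stratifies by site, and 10.5 does not say whether the mixed model reflects it. If site is omitted and sites differ after baseline adjustment, the analysis is conservative to the extent shown above; at ICC 0 nothing is lost. The sizes rest on assumed ICCs, correlations, dropout and block sizes. The direction follows from the design.

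Stronger readings are tempting but unsupported. Leaving site out does not bias the comparison and does not raise the false-positive rate; it lowers it. It does not undermine the 80% in 10.1, which reproduces and does not fall as site differences grow. Nor is it mainly a loss of true precision, since the empirical SD changes by only 0 to about 2%. The mixed-model 3-month results are secondary endpoints, and the analyses of return to activities and return to work are not affected.

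**What to change.** In 10.5, state that the mixed model for BCTQ-SSS, BCTQ-FSS, Numeric Pain Scale and EQ-5D-5L includes site in addition to the baseline score, and whether site is fixed or random. A random site intercept is suggested; when the site variance is estimated as zero, it reduces to the model without site. Leave the Fisher's exact and Mann-Whitney tests as they are, and add no site-stratified versions of them.

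The cost is one sentence, plus the IRB submission that 11.9.2 requires for any protocol change. No extra subjects or data are needed. If sites do not differ, a random intercept costs essentially no power at 0.50 SD (78.6 without against 78.9% with, equal sites; 78.2 against 78.5%, uneven sites). Its reported SE is then about 1% low (0.1781 against 0.1801), and null rejection with site in the model ran from 4.4 to 5.7% across layouts. Fixed site effects would cost up to about 1 point (78.6 to 78.0%, and 78.2 to 77.2%).
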